The pharmacovigilance plan includes setting up a patient registry of type 2 diabetic patients taking lixisenatide. This would represent a proactive risk assessment in the post approval setting that allows for prospective follow-up and monitoring of occurrences of any of the outcomes of interest, i.e. pancreatitis, pancreatic cancer and thyroid cancer (especially medullary carcinoma of the thyroid).

The registry population will be representative of the population actually using the product since it should include all patients regardless of age, comorbidities or concurrent treatments. Follow up duration will be long enough to encompass delayed risks, consequences of long term use and effects of various combinations and alternations of treatments if any.

III.8 Research Question and Objectives

Study objectives

In the context of pharmacovigilance activity of the EU RMP (European Union Risk Management Plan), it has been agreed with the European Medicines Agency (EMA) to develop a Patient Registry of patients with diabetes exposed to lixisenatide.

The primary objectives of this study are to monitor the occurrences of:

- 1. acute pancreatitis,
- 2. pancreatic cancer
- 3. thyroid cancer, especially medullary carcinoma of the thyroid,

among adult type 2 diabetes patients treated with lixisenatide and to compare their risks with that of users of (1) other GLP-1 receptor agonists from the Database Study ; (2) other diabetic medications from the Database Study; and (3) the general population. The assembled cohort will be constantly monitored for these events to detect and emerging signal as quickly as possible.

Declaration of Study Hypotheses

This study is designed to focus on the risk associated with use of lixisenatide and will investigate the following primary hypotheses:

- 1. That adult patients prescribed lixisenatide have an increased risk of acute pancreatitis when compared to the expected risk calculated for the other GLP-1 RA users;
- That adult patients prescribed lixisenatide have an increased risk of pancreatic cancer when compared to the expected risk calculated for the other GLP-1 RA users;
- 3. That adult patients prescribed lixisenatide have an increased risk of thyroid cancer (especially medullary carcinoma of the thyroid) when compared to the expected risk calculated for the other GLP-1 RA users;

Comparison of the incidence of these three conditions among users of lixisenatide and users of other GLP-1 receptor agonists will be available from the companion study among databases. This will provide an important background when interpreting any Odds Ratio found.

- 4. That adult patients prescribed lixisenatide have an increased risk of pancreatitis when compared to the expected risk calculated for other diabetic medications (which will also be divided into groups of oral medications (an indicator of less severe diabetes) and insulin (an indicator of more severe diabetes);
- That adult patients prescribed lixisenatide have an increased risk of pancreatic cancer when compared to the expected risk calculated for other diabetic medications (which will also be divided into groups of oral medications (an indicator of less severe diabetes) and insulin (an indicator of more severe diabetes);
- 6. That adult patients prescribed lixisenatide have an increased risk of thyroid cancer (especially medullary carcinoma of the thyroid) when compared to the expected risk calculated for other diabetic medications (which will also be divided into groups of oral medications (an indicator of less severe diabetes) and insulin (an indicator of more severe diabetes);

What is requested is to monitor the occurrence of pancreatitis, pancreas cancer and thyroid cancer in patients with diabetes receiving lixisenatide and to identify any potential signal indicating an increased level of pancreatitis, pancreas cancer and thyroid cancer as reliably and as quickly as possible. Comparisons need to be made with the background rate in patients with diabetes and also the general population before conclusions can be drawn. [Patients with diabetes have a background increased risk of both pancreatitis and pancreas cancer].

The comparison between risk of outcome events with different treatments will require to be handled very carefully. The only way to make such comparisons in an unbiased manner would be via a randomised clinical trial. In the observational studies proposed herein there are other factors, such as patient characteristics and physician choice, which may influence treatment choice. The products in question will not be distributed to patients in a randomised manner.

Importantly, comparison of risk of the endpoints (Pancreatitis, Pancreas Cancer, Thyroid cancer) in this setting is fraught with hazard particularly when comparing patients receiving lixisenatide with the use of all other anti-diabetic medications. This latter group will comprise a group of patients with a wide range of treatments associated with diabetes of different durations and different levels of severity, from less severe (e.g. patients prescribed metformin) to more severe (e.g. patients with basal and prandial insulins). Care will be taken to separate this group into patients with oral anti-diabetic medications and those requiring insulin: at least this will provide two comparison groups at different levels of diabetes severity.

A comparison of cases observed and the numbers observed given the rates in the general population will also be made although there are quite severe issues regarding comparability of the groups which make interpretation complicated. The observation periods are not contemporaneous which introduces a potential source of confounding and/or information bias arising from potential differential diagnostic accuracy in the two time periods. This will be addressed in the statistical analysis and interpretation.

III.9 Research Methods

III.9.1 Study design

This will take the form of a Patient Registry involving patients treated with lixisenatide in Denmark, Norway and Sweden. Additional sources of data will be sought among leading diabetes centres to identify more detailed clinical information. The study design will be the same in all 3 countries, but the data management procedure will differ between the centres, therefore some 'technical' details of the study implementations will be properly defined after consultation with each separate centre.

Prior to the full Registry study commencing, it will be essential to determine the most efficient manner in each country to develop the Register and to obtain the follow-up information. During this phase, it will be possible to refine the study design and, particularly, the methodology employed in each country.

III.9.2 Setting

The study will be based in Denmark, Norway and Sweden. These countries have been chosen because each has:

- 1. A high-quality prescription registry that is population-based.
- 2. A high-quality cancer registry, which covers the entire population included in the prescription database.
- 3. A national hospital discharge registry, which covers the entire population included in the prescription database
- 4. A national death register, which can be used for record linkage to ascertain the date of death of any patient in the patient registry who died.
- 5. A source of information on key confounders (notably BMI), either in the prescription database itself, in a diabetes registry or in other available databases or large prospective studies.

A unique personal identity number will be used to link together the information from the several population based registries, as shown in the figure below:

The source of the cohorts will be mainly represented by the drug prescription registries.

The study population will include patients with type 2 diabetes treated with lixisenatide after launch. The study period will start from the lixisenatide launch and last for 5 years.

The patients will be identified as having been prescribed at least one prescription for the GLP-1 RA lixisenatide.

High completeness of follow-up is expected, as well as high accuracy of data, which will allow capture of the variables of most interest.

The study entry date will be defined as the date of the first prescription of lixisenatide after launch. The follow-up will end at the earliest of the following: 1) death or 2) the end of the register.

Data from national registers and databases in Denmark, Norway and Sweden will be used as the primary data source to identify lixisenatide treated patients for this registry. In Denmark, Norway and Sweden, national prescription databases have been established and are linkable to other national registers and databases (e.g., National Cancer Registry, Cause of Death Registry, and Hospital Discharge Registry) via National Registration Identification number.

A detailed table of characteristics of the cohort included in the analysis will be provided after consultation with the local investigators.

III.9.3 Variables (Outcome, Exposure, Risk factors, Confounding variables)

For each patient, information regarding all anti-diabetic medications prescribed in the study period will be recorded together with basic information such as age and gender.

Patients who develop pancreatic cancer and thyroid cancer will be identified as well anyone who is diagnosed with pancreatitis, and their complete clinical information will be retrieved and collected from existing national registers and databases annually: smoking history, a previous diagnosis of Multiple Endocrine Neoplasia (especially MEN1), chronic pancreatitis, duration of diabetes, gallstones, prior use of other anti-diabetics, alcohol intake, obstruction of the pancreatic duct, radiation treatment to the head and neck, iodine intake, hormonal and reproductive treatment, diagnosis of Multiple Endocrine Neoplasia type 2 (MEN2), history of goitre or benign thyroid nodules, history of cancer, and family history of medullary thyroid cancer.

Outcomes of interest

Acute pancreatitis cases will be identified from the hospital discharge registers. Cases of thyroid cancer and pancreatic cancer will be identified from the national cancer registers. However, data on the cancer cases for a given year are typically considered incomplete until approximately one year after the year ends. For example, it will be possible to use the national cancer registries to identify incident cancers occurring until the end of 2013, if the analysis of thyroid cancer is planned to be performed in early 2015.

Exposure assessment and follow-up time

Patients with one or more prescriptions of lixisenatide will be identified from the national prescription registers and included in the register.

For acute pancreatitis, the exposure duration on lixisenatide will begin accumulating on the first day of lixisenatide prescription and continue with the subsequent continuous use of lixisenatide until:

- 1) the end of the lixisenatide treatment (in addition to a grace period of up to 30 days, to account for non-adherence),
- 2) the occurrence of acute pancreatitis, or;
- 3) the end of registry, whichever comes first.

For thyroid cancer and pancreatic cancer, the exposure duration will start from the first day of lixisenatide prescription and continue until either (1) the occurrence of thyroid cancer or pancreatic cancer, or (2) the end of registry, whichever comes first.

III.9.4 Data Sources

Patient registry data sources are the same as for the data base study (Section II.9.4)

Patients will be identified in the National Prescription Database. They will be linked to the National Death Indices, National Cancer Registries and National Hospital Discharge schemes to identify cases of cancer, pancreatitis and anyone who has died. Clinical data for all patients with the outcome of interest will also be retrieved from National Hospital Discharge schemes. Additional data will be collected from other (country specific) available data sources.

The personal identification number will be used to link unambigously the databases in each country. The ATC coding system (Anatomic Therapeutic Coding) will be used to identify exposure: all patients having been prescribed drugs for the treatment of diabetes (ATC code A10 and subcategories) will be retrieved and linked to the other databases: they will be followed via cancer and hospital discharge registries. The ICD10 codes will be used for outcome assessment: acute pancreatitis (K85), pancreatic cancer (C25) and thyroid cancer (C73), especially medullary thyroid cancer.

III.9.5 Study Size

All available data following the launch of lixisenatide will be analyzed for the final analyses. The data from the three participating countries will be combined together for the analysis. The estimation of sample size and study power for the objectives of this study will be further defined after consultation with local Principal Investigators and external experts.

According to estimates provided by the International Diabetes Federation for 2013, there were 1,049,810 prevalent cases of diabetes among adults aged 20-79 in the three countries combined (346,730 in Denmark; 209,870 in Norway; and 493,210 in Sweden). In addition, assuming a crude incidence rate of diabetes of 364 per 100,000 personyears (calculated using data for 1995-2006, from Carstensen et al, 2008), then for a total adult population of 15,000,000 persons, approximately 55,000 new cases of diabetes will be diagnosed every year in the three countries combined. This provides an estimate of the numbers of new cases of diabetes that are potentially eligible for the study. Not all of these patients will be candidates for treatment with lixisenatide for a variety of reasons. However, various scenarios about the prevalence of patients prescribed lixisenatide are made in order to estimate the statistical power of the Registry study. These estimates are presented in Table III.9.5.1 and Table III.9.5.2.

Using these hypothetical numbers, the number of patient-years accumulated over a period of 5 years of registry were calculated as follows:

1st year of registry: no records yr1 = %lixi * prevalence diabetes = %lixi * 1,049,810 2nd year of registry: no records yr2 = no records yr1 + new records yr2= no_records_yr1 + %lixi * new_cases_diabetes = no_records_yr1 + %lixi * 55,000 3rd year of registry: no_records_yr3 = no_records_yr2 + new_records_yr3 = no_records_yr1 + 2 * %lixi * new_cases_diabetes

etc...

Thus the number of person-years accumulated over 5 years is: Person-years_over_5_years = no_records_yr1 + no_records_yr2+..+ no_records_yr5 =5*(%lixi*prevalence_diabetes)+10*(%lixi*new_cases_diabetes)

The number of expected cases of pancreatitis were calculated using the incidence rate shown above (65.57 per 100,000 person-years). The power of the study was then calculated for the expected number of cases as a mean of Poisson law (Breslow and Day, 1987) and a range of expected vs observed ratios. The results are shown in Table III.9.5.1.

Table III.9.5.1: Estimates of statistical power for Registry Study for pancreatitis under different scenarios for prevalence of prescription of lixisenatide.

Pancreatitis (incidence rate=65.57/100,000 pyrs)						
	Pyrs No of Power in order Power in order Power in o					
% exposure to	accumulated	expected	to detect	to detect	to detect	
lixisenatide	over 5 years	cases	obs/exp+=1.2	obs/exp+=1.5	obs/exp+=2	
0.10%	5799.05	3.8	0.10*	0.17	0.39	
0.20%	11598.1	7.6	0.13*	0.26	0.64	
0.50%	28995.25	19.0	0.18	0.60	0.97	
0.80%	46392.4	30.4	0.27	0.79	1.00	
1.00%	57990.5	38.0	0.29	0.83	1.00	
1.50%	86985.75	57.0	0.37	0.93	1.00	
2%	115981	76.0	0.47	0.98	1.00	
5%	289952.5	190.1	0.38*	1.00	1.00	
10%	579905	380.2	0.60*	1.00	1.00	
*Calculated using normal approximation						
tobs /exp stands for 'observed us expected ratio'						

+obs/exp stands for 'observed vs expected ratio

These numbers are certainly underestimated, as the incidence of diabetes has been steadily increasing worldwide. Even so, for a 1% exposure to lixisenatide among diabetic patients, thus 38 expected cases of pancreatitis, the power of the study in order to

detect an observed vs expected ratio of pancreatitis of 1.5 will be of 83% (significance level=0.05).

Table III.9.5.2 shows the power calculation for the Patient Registry Study and cancer (pancreatic cancer and thyroid cancer). For 1% of exposure to lixisenatide among the diabetic population the study will be able to detect an observed vs expected ratio of pancreatic cancer of 1.5 with 59% power (significance level=0.05), and an observed vs expected ratio of 2 with 92% power (significance level=0.05). For 1% exposure to lixisenatide, the study is underpowered to detect these same ratios of thyroid cancer, it will be able to detect with power of 92% an observed vs expected ratio of 2 (significance level=0.05) for 5% exposure to lixisenatide among the diabetic population.

Table III.9.5.2 : Estimates of statistical power for Registry Study for pancreas cancer and thyroid cancer under different scenarios for prevalence of prescription of lixisenatide.

Pancreatic cancer (incidence rate=29.19/100,000 pyrs)				
	Pyrs	No of	Power in order	Power in order to
% exposure to	accumulated	expected	to detect	detect
lixisenatide	over 5 years	cases	obs/exp+=1.5	obs/exp+=2
0.10%	5799.05	1.7	0.07	0.14
0.20%	11598.1	3.4	0.17	0.39
0.50%	28995.25	8.5	0.32	0.73
0.80%	46392.4	13.5	0.48	0.90
1.00%	57990.5	16.9	0.59	0.92
1.50%	86985.75	25.4	0.74	>0.98
2%	115981	33.9	0.79	1.00
5%	289952.5	84.6	0.99	1.00
10%	579905	169.3	1.00	1.00
	Thyroid cancer (incidence rate	=6.13/100,000 py	rs)
	Pyrs	No of	Power in order	Power in order to
% exposure to	accumulated	expected	to detect	detect
lixisenatide	over 5 years	cases	obs/exp+=1.5	obs/exp+=2
0.10%	5799.05	0.4	<0.07	<0.14
0.20%	11598.1	0.7	<0.07	<0.14
0.50%	28995.25	1.8	0.07	0.14
0.80%	46392.4	2.8	0.08	0.21
1.00%	57990.5	3.6	0.17	0.39
1.50%	86985.75	5.3	0.22	0.54
2%	115981	7.1	0.26	0.64
5%	289952.5	17.8	0.59	0.92
10%	579905	35.5	0.83	1.00
+obs/ovp stands	for 'obsorved us	whether a the		

+obs/exp stands for 'observed vs expected ratio'

Thus, a prevalence of 0.08% of patients with diabetes prescribed lixisenatide would give the study an 80% power to detect a risk of 1.5. Similar calculations reveal that for pancreas cancer the corresponding prevalence of lixisenatide prescription to give 80% power would be 2% and for thyroid cancer 9%.

III.9.6 Data Management

Once the study population well defined via prescription registries, it will be essential to collect the follow-up data efficiently.

Adequate training of the staff will be essential in order to correctly recognize and report all events of interest. Systematic collection of follow-up data, routine follow-up of all registry patients for the key adverse effects previously identified, as well as all other information.

In each centre data will be linked between the different data sources (population registry, prescription registry, hospital discharge registry, cancer registry) through an anonymized unique identification number. Linking the population registry, the prescription registry and the cancer registry has already been tested and proved to be effective through our previous database study (Boyle et al, 2013). However, linking with the hospital discharge registry requires a procedure preventing introduction of information bias in the study.

All patients identified to have had an anti-diabetic treatment in the prescription database (regardless of the type of medication taken) will be linked to the Hospital Discharge Registry. All discharge information will be retrieved for all the diabetic patients (with an anti-diabetic prescription) and searched for codes or keywords that indicate a pancreas related disease. For the purpose of this task, in each country a Medical Adjudication Committee (MAC) will be assembled, composed of at least two internists, who will be blinded as to treatments taken by patients. The MAC will examine all charts of potential pancreatitis patients receiving lixisenatide and also patients receiving other GLP-1 receptor agonists. They will be responsible for:

- Establishing a disease definition for acute pancreatitis²;
- Identify codes or keywords in hospital discharge records possibly associated with pancreatitis;
- Contact hospitals (through a standardized questionnaire) for getting full information on the data the diagnosis of pancreatitis was based on
- Review data for establishing whether pancreatitis was present.

After that the MAC assessment will be entered in the study database, the analyses in function of the treatment type (lixisenatide, other GLP-1 RAs or other anti-diabetic drugs) will be made following a review by the MAC of some patients not thought to have pancreatitis (to confirm the absence of the disease).

² An external blinded committee (Pancreatic Safety Assessment Committee or PSAC) has been appointed to review all pancreatic adverse events occurring in clinical trials of lixisenatide. The PSAC Charter has not been finalized, yet. However, the criteria for adjudication of acute pancreatitis will be adapted from those proposed by Banks, Freeman, and the Practice Parameters Committee of the American College of Gastroenterology (Am J. of Gastroenterology 2006;101:2379-2400) and Frossard et al. (Lancet 2008;371:143-52.).

Similarly to the Database Study, each national centre will be responsible for the data storage and data management of the individual-level data, following all national and European directives regarding the well being and rights of each study subject. Each centre has an excellent track record of successfully undertaking similar research respecting all moral and legal requirements.

Only de-identified data will be stored at IPRI, and this will be done in a secure manner: data will password protected, and stored on local machines.

III.9.7 Data Analysis

Descriptive analysis will be performed and total follow-up time for lixisenatide users will be calculated.

Figure II.9.7.3: General study overview

For acute pancreatitis, pancreatic cancer and thyroid cancer, the expected number of cases will be estimated annually after launch using the background rates obtained from the retrospective databases study.

If the observed number of cases for the events of interest, respectively, is significantly higher than the expected number of cases, further investigation may be warranted following discussion with the regulatory authorities.

An independent **Scientific Steering Committee** will be appointed to oversee the study and advise on treatment, methodological and biostatistical issues. This group will meet regularly throughout the duration of the study and incorporate a **Biostatistical Advisory Group**, to advise on all aspects of the design and data analysis.

The Scientific Steering Committee will comprise:

[name] University of Perugia Perugia, Italy

[name] University College London London, United Kingdom

[name] Robertson centre for Biostatistics University of Glasgow, Glasgow, United Kingdom

[name] Department of Biostatistics Yale University School of Public Health New Haven, United States of America

[name] McMaster University, Hamilton, Canada

[name] Mount Sinai Hospital New York, United States of America.

A Medical Adjudication Commitee (MAC), comprising of at least 2 medical internists in each country will be appointed. Their role will be to: 1) Establish the case definition for acute pancreatitis; 2) identify codes and keywords related to pancreatitis 3) Communicate with hospitals for data on diagnosis; 4) Verify the diagnosis on the basis of information transmitted by hospitals.

Research Institute

III.9.9 Limitations of Research methods

Several issues relating to confounding should be overcome by the prospective registry design. Although not a randomised study, this registry study will enable significant progress to be made over and above a classical database study. In particular, there will be the opportunity to have better information about the basis of the diagnoses of interest and also access to information about the patient's diabetic history and treatment, issues such as why a particular treatment choice was made and why any change was made to treatment will be accessible. The study will also allow methodological investigations of differences between the retrospective database studies being conducted in the same populations and the prospective Register study.

Protection of Human Subjects III.10

Each national centre will be responsible for following all national and European directives regarding the well-being and rights of each study subject. Each centre has an excellent track record of successfully undertaking similar research respecting all moral and legal requirements. At the central office (iPRI, Lyon) no identifiable data will be received from the individual centres.

III.11 Management and Reporting of adverse events/reactions

All approvals necessary to undertake this study will be obtained in each country. In addition, the study protocol and the national approvals will be submitted to the IPRI Ethics Committee who will give tertiary ethical approval.

Reporting of adverse events or adverse reactions on individual patients is not appropriate to this form of study where there is no contact between the investigators and the patients.

III.12 Plans for disseminating and communicating study results

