For data analysis, a two stage process will be adopted because it is not possible to share individual level data. In each country an individual level analysis will be carried out using a common statistical methodology. The anonymous results (statistical model coefficients) will be transferred to the coordinating center IPRI in a secured way (password protected). Pooling of the within study effects in a meta-analysis (Thompson et al, 2010), will then be carried out at I-PRI. This same procedure was used successfully in the earlier study. Notably, no identifiable data will be made available outside the country where the data are obtained.

II.9.7 Statistical Analysis

Full details of the statistical analysis will be determined prior to the end of the period of data collection and discussed and approved by the Biostatistics Advisory Committee. This is in a similar manner to the approach adopted in the *Northern European Database Study of Glargine and Cancer* (Boyle et al, 2013). The philosophical approach to the statistical analysis will be in the spirit of this previous study, whose statistical analysis plan is attached as Appendix III.

1. Incidence rates and 95% confidence intervals (CI) of pancreatitis, pancreatic cancer and thyroid cancer among the patients treated with GLP-1 RAs as well as those patients treated with other anti-diabetic medications will be derived. In addition, fitting a Poisson regression model may be considered.

2. Hazard ratios (95% CIs) of pancreatitis, pancreatic cancer and thyroid cancer associated with the treatment of GLP-1 RAs versus other anti-diabetics will be estimated using time-dependent Cox proportional hazards survival analysis. The potential confounding factors listed above will be adjusted for in the analyses (to be further discussed and refined by external experts).

The two types of analyses above (intent-to-treat analysis and an analysis by censoring the follow up time at the end of treatment of either GLP-1 RAs or other anti-diabetics) will be stratified by age, sex, previous anti-diabetic treatments (such as insulin, metformin etc) and other confounding factors in function of their availability.

3. Profile of GLP-1 users as compared to users of other anti-diabetics, for instance: age, sex, previous prescriptions, further covariates when available.

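### Hypotheses 4-6 of the Registry divide the comparator by insulin use but not the lixisenatide cohort, so the oral and insulin sub-comparisons are biased in opposite directions if event rates differ by insulin status

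*Protocol*

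**What the plan says.** Hypotheses 4-6 in Protocol III.8 state that lixisenatide users have a raised risk of pancreatitis, pancreatic cancer and thyroid cancer relative to the risk expected from users of other antidiabetic drugs. Of this comparator group each hypothesis adds: "which will also be divided into groups of oral medications (an indicator of less severe diabetes) and insulin (an indicator of more severe diabetes". The discussion that follows in III.8 repeats the division for the comparator: "Care will be taken to separate this group into patients with oral anti-diabetic medications and those requiring insulin".

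On the lixisenatide side, III.7 says of the Registry population that "it should include all patients regardless of age, comorbidities or concurrent treatments". III.9.6 lists lixisenatide as one treatment type: "the analyses in function of the treatment type (lixisenatide, other GLP-1 RAs or other anti-diabetic drugs) will be made". III.9.7 says that "the expected number of cases will be estimated annually after launch using the background rates obtained from the retrospective databases study" and names no strata.

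The data needed for a matched comparison are collected. III.9.3 says "For each patient, information regarding all anti-diabetic medications prescribed in the study period will be recorded". In the Database Study, II.9.7 says that the analyses "will be stratified by age, sex, previous anti-diabetic treatments (such as insulin, metformin etc"), and II.9.3 also plans stratification by treatment history. Neither is carried into the Registry's expected counts.

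**The concern.** The protocol recognises that the group on other antidiabetic drugs mixes patients of different severity, and its remedy is to divide that group by oral drugs and insulin. Dividing one side of a comparison does not make the two sides alike. Lixisenatide users who also take insulin are counted against the rate for oral users, and lixisenatide users without insulin are counted against the rate for insulin users.

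If the event rate differs by insulin status, the two sub-comparisons depart from 1 for a drug with no effect, one upwards and one downwards. A raised ratio against oral users may then reflect the severity mix alone, and a real excess may disappear against insulin users. The protocol gives no rule for reading the two when they disagree. A significant excess is what would prompt discussion with regulators about further investigation, so the bias bears on the Registry's signal function.

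**Working it through.** **Inputs from the protocol (III.9.5).** Prevalent diabetes 1,049,810; 55,000 new cases a year; 5 years; 1% exposure. For the rate: "The number of expected cases of pancreatitis were calculated using the incidence rate shown above (65.57 per 100,000 person-years").

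Person-years = 0.01 × (5 × 1,049,810 + 10 × 55,000) = 57,990.5. Expected cases E = 57,990.5 × 65.57/100,000 = 38.02, which matches the stated 38.

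**The plan's own power figure.** It states 83% for a ratio of 1.5 at significance level 0.05, with sidedness not given. An exact one-sided 5% Poisson test at E = 38.02 rejects at 49 or more cases (true size 0.049) and has power 0.872. A two-sided normal approximation gives 0.820. The exact one-sided test at E = 35 gives 0.833, so the table may rest on a rounded-down expected count. The stated figure is close enough to serve as a base, and it is not itself in dispute.

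**Model for the sub-comparisons.** Let p be the share of lixisenatide person-time on insulin and r the insulin/oral event-rate ratio. For a drug with no effect:

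- against the oral rate, observed/expected = 1 + p(r − 1);
- against the insulin rate, observed/expected = [1 + p(r − 1)]/r;
- against the undivided comparator with insulin share q, observed/expected = [1 + p(r − 1)]/[1 + q(r − 1)].

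With r > 1 and 0 < p < 1, the first is above 1 and the second below 1. If r = 1 there is no bias. If r < 1 the directions reverse.

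**Numbers.** The documents give neither p nor r, so the ranges below are assumptions. E = 38.02 is used for whichever comparator is tested, as an illustration, with a signal at 49 or more cases.

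| r | p | Null ratio, oral | False-signal rate, oral | Null ratio, insulin | Power for true 1.5, insulin |
|---|---|---|---|---|---|
| 1.25 | 0.2 | 1.05 | 0.09 | 0.84 | 0.46 |
| 1.25 | 0.6 | 1.15 | 0.23 | 0.92 | 0.70 |
| 1.5 | 0.4 | 1.20 | 0.33 | 0.80 | 0.33 |
| 2.0 | 0.2 | 1.20 | 0.33 | 0.60 | 0.01 |
| 2.0 | 0.6 | 1.60 | 0.95 | 0.80 | 0.33 |

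For example, with r = 1.5 and p = 0.4 the oral ratio is 1 + 0.4 × 0.5 = 1.20 and the insulin ratio is 1.20/1.5 = 0.80. A true 1.5-fold effect then reads as 1.5 × 0.80 = 1.20 against insulin users.

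**Undivided comparator.** With r = 1.5, p = 0.4 and q = 0.2 the null ratio is 1.20/1.10 = 1.09. With p = q it is 1.00.

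**After matching on insulin status.** The null ratio is 1.00 with respect to insulin mix, the size is 0.049, and power at a true ratio of 1.5 is 0.872 on the total count.

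**The case against.** The protocol does not hide the difficulty. III.8 says that an unbiased comparison would need randomisation, warns that this one is hazardous, and claims for the division only that it yields two comparison groups of different severity. Under the model above, a null cohort lies between the oral and insulin rates, so the pair works as a bracket: exceeding even the insulin rate is strong evidence, and falling below the oral rate is reassuring. That stands, and it is a reason to keep both comparisons in view.

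Three stronger readings are tempting, and the documents do not support them. A reader might infer that every ratio in hypotheses 4-6 is biased. The hypotheses say the comparator will *also* be divided, so there is a first comparison with the undivided group, mixed against mixed, which is biased only if the insulin shares differ. A reader might infer that a significant sub-comparison sets off an investigation automatically. The protocol says only that one may be warranted after discussion with the regulatory authorities. And a reader might infer that insulin itself causes the distortion, or that insulin users are known to have higher rates of each outcome. The protocol treats insulin as a marker of severity and gives no event rates by insulin status.

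It can also be said that stratification of expected counts belongs in an analysis plan, which is not at hand. That would answer a mere silence. Here the one-sided division is written into the declared hypotheses and repeated as the remedy, so it is a choice the protocol has made.

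**Conclusion.** The point holds for the two sub-comparisons of hypotheses 4-6. The protocol applies its own severity marker to the comparator and not to a lixisenatide cohort that is mixed by design. The opposite directions of bias follow from that design whenever event rates differ by insulin status.

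The size cannot be derived from the documents. The ranges in the working depend on the assumed insulin share and rate ratio, on a one-sided test, and on using 38 expected cases, which come from an overall rate and not from an oral-user or insulin-user rate. They show that even the mildest combination nearly doubles the nominal error rate against oral users (0.09 against 0.049). The stated 83% power refers to an overall expected count and is unaffected. This should be corrected, but it does not undermine the Registry as a whole: hypotheses 1-3, against other GLP-1 receptor agonist users, do not use this division.

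**What to change.** In III.8 and III.9.7, classify lixisenatide person-time by insulin use. Compute the expected count for each part from the Database Study rate for comparator patients of the same insulin status, by age and sex. Make the summed observed against the summed expected count the main comparison for hypotheses 4-6, and show the two strata beside it. The comparisons of the whole lixisenatide cohort with the oral rate and with the insulin rate may stay as descriptive brackets, but not as signal tests.

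No new patient data are needed, because every lixisenatide user's antidiabetic prescriptions are already recorded. The cost falls on the Database Study: its centres, which plan to transfer model coefficients, must also supply rates by age, sex and insulin status. The stratum-specific ratios will be less precise, although the summed test keeps all cases.
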